**CONFIDENTIAL**

056-F275 Rev E Clinical Investigation Plan Template

3. Introduction

Medtronic, Inc. is sponsoring the Reveal LINQ™ for COPD study. This study will be referred to by LINQ™ for COPD in this document. This is a Non-Significant Risk Investigational Device Exemption (IDE), prospective, non-randomized, multi-center, observational, pre-market clinical study.

The purpose of the study is to collect and characterize Reveal LINQ™ derived data from patients with COPD by assessing the relationship between changes in LINQ™ derived data with COPD exacerbation events. The study will also collect information regarding COPD related clinical events during the same period.

The study is utilizing the Reveal LINQ™ device with an investigational LINQ-HF RAMware download. The Reveal LINQ™ device is designed to automatically record the occurrence of ventricular tachyarrhythmias, bradyarrhythmias, pause, atrial tachyarrhythmias, and atrial fibrillation. The patient is

also able to activate the insertable cardiac monitor (ICM) to record their cardiac rhythm while experiencing or immediately after a symptomatic event. In addition, the LINQ™-HF RAMware enables the hardware to record and store impedance, temperature, activity, respiration rate (RR) interval, R-wave amplitude, posture change count (based on z-axis accelerometer values) and x, y, and z-axis accelerometer measurements periodically.

Following consent, subjects will undergo a baseline assessment followed by the LINQ™ ICM device insertion procedure. Following insertion, subjects will complete a daily diary entry, which includes answering the Breathlessness, Cough, and Sputum Scale (BCSS) Questionnaire and recording any pro re nata (PRN) medications. Additionally, subjects will complete telephone follow-up visits every three months post device insertion (visits may also be conducted in-person if desired). The 6-month follow-up visit however, will need to be conducted in office. Study subjects will be followed until the last enrolled subject reaches their 12-month visit or until official study closure defined as when Medtronic and/or regulatory requirements have been satisfied per the Clinical Investigation Plan and/or by a decision by Medtronic or regulatory authority, whichever occurs first.

This Statistical Analysis Plan has been designed to document, for internal use, the LINQ™ for COPD study design and the planned analyses to be included in a final report.

4. Study Objectives

The study objective has been defined to characterize the Reveal LINQ™ derived data in patients with COPD related to COPD events.

The study objective will be characterized, and a final study report will be completed after the last enrolled subject is followed for 12-months or study closure, whichever occurs first.

4.1 Primary Objective

The primary objective is to characterize Reveal LINQ™ derived data from patients with COPD by assessing the relationship between changes in LINQ™ derived data with subsequent COPD events.

COPD event is defined as an adverse event where the underlying COPD condition exacerbates beyond normal day-to-day variations, where an increase in dyspnea, cough, and/or sputum production presents with acute onset and necessitates supplementing regular COPD medications with antibiotics for respiratory pathogens and/or steroids.

5. Investigation Plan

The LINQ™ for COPD is a prospective, non-randomized, multi-center, observational, pre-market clinical study. The study may enroll up to 100 COPD subjects at up to 10 sites in the US, with no more than 20 subjects enrolled per site. Study subjects will be followed until the last enrolled subject reaches their 12-month visit or until official study closure defined as when Medtronic and/or regulatory requirements have been satisfied per the Clinical Investigation Plan and/or by a decision by Medtronic or regulatory authority, whichever occurs first. Accordingly, the expected total study duration is approximately 25 months, representing approximately 12 months of patient enrollment and 12 months of subject follow-up with 1 month between enrollment and insertion. All Reveal LINQ™ system and procedure-related adverse events will be collected and reported per the study protocol. In addition, all SAEs, all Respiratory related AEs (regardless of seriousness) and all Cardiovascular related AEs (regardless of seriousness) will be collected and reported per study protocol.

Following consent, subjects will undergo a baseline assessment followed by the LINQ™ ICM device insertion procedure. Following insertion, subjects will complete a daily diary entry, which includes answering the BCSS Questionnaire and recording any PRN medications. Additionally, subjects will complete telephone follow-up visits every three months post device insertion (visits may also be conducted in-person if desired). The 6-month follow-up visit however, will need to be conducted in office. All enrolled subjects will be followed until study closure. A study flowchart is shown in Figure 1.

[figure not shown]

Figure 1: Study Flowchart

The subject population for the LINQ™ for COPD study is COPD patients who are known to have frequent exacerbations (at least two in the past year). Inclusion and Exclusion criteria are listed below.

5.1 Inclusion Criteria

- Patient is ≥ 45 years old
- Patient (or patient's legally authorized representative) is willing and able to provide written informed consent
- Patient is willing and able to comply with the protocol, including follow-up visits, electronic diary submissions and CareLink transmissions
- FEV₁ (post bronchodilator) $\leq 70\%$ of predicted

- Current or former smoker with lifetime cigarette consumption of \geq 10 pack-years
- Two COPD exacerbations within the previous 12 months defined as taking antibiotics and/or prednisone for respiratory symptoms, hospitalization or emergency department visit for respiratory illness.
- The patient's medical records must be accessible by the enrolling site over the follow-up period

5.2 Exclusion Criteria

- Less than 30 days from treatment from a COPD exacerbation as defined as taking antibiotics and/or prednisone for respiratory symptoms, hospitalization or emergency department visit for respiratory illness.
- Less than 30 days from treatment from a HF event as defined as any cardiovascular-related (including hypervolemia) Health Care Utilizations (HCUs) for any one of the following events.
 - Admission with primary diagnosis of HF
 - Intravenous HF therapy (e.g. IV diuretics/vasodilators) or ultrafiltration at any one of the following settings:
 - Admission with secondary/tertiary diagnosis of HF
 - Emergency Department
 - Ambulance
 - Observation Unit
 - Urgent Care
 - HF/Cardiology Clinic
- Active respiratory infection being treated by health care professional.
- Class IV heart failure
- Clinical diagnosis of unstable angina, asthma, bronchiectasis, or cystic fibrosis
- Any concomitant condition that might endanger the patient through participation in the study or interfere with study procedures, as assessed by the investigator
- Patient is pregnant (all females of child-bearing potential must have a negative pregnancy test within 1 week of enrollment)
- Patient is enrolled in another study that could confound the results of this study, without documented pre-approval from a Medtronic study manager
- Patient has an existing or planned implantation of Medtronic IPG, ICD, CRT-D or CRT-P device in the near future
- Patient has an existing and active insertable cardiac monitor, regardless of manufacturer
- Concurrent disease with life expectancy less than 1 year

6. Determination of Sample Size

There are no sample size requirements as this is an observational study with no hypothesis for the study objective. A sample size of up to 100 enrolled subjects was selected assuming sufficient data can be collected from this cohort to explore the relationship between changes in LINQ™ derived data with COPD events.

According to a review by Seemungal et al., the annual rates of COPD exacerbations were estimated to be as low as 0.5 to a high of 3.5 exacerbations per patient from several studies, and hospitalization rates ranged from as low as 0.09 to 2.4 per patient per year.¹ This study requires that a subject should have 2 COPD exacerbations within the previous 12 months as one of the inclusion criteria. Assuming the COPD exacerbation rate remains as 2 COPD exacerbations per patient year after subjects are enrolled, a group of 60 enrolled subjects being followed up for 12 months after successful insertion of Reveal LINQ™ device and download of LINQ™ HF investigational RAMware would expect to have 120 COPD exacerbations. Assuming 50% of the COPD exacerbations would meet the study definition of “COPD event”, a total of 60 COPD events would be expected.

A COPD event is defined as an adverse event where the underlying COPD condition exacerbates beyond normal day-to-day variations, where an increase in dyspnea, cough, and/or sputum production presents with acute onset and necessitates supplementing regular COPD medications with antibiotics for respiratory pathogens and/or steroids.

7. Statistical Methods

7.1 Study Subjects

7.1.1 Disposition of Subjects

This is a single-arm study. A subject will be considered enrolled in the study once they sign and date the Informed Consent. Following consent, subjects will undergo a baseline assessment followed by the Reveal LINQ™ ICM device insertion procedure. After the device is inserted, the LINQ™ HF investigational RAMware will be downloaded to the device via the 2090 programmer. Following insertion, subjects will also complete a daily diary entry, which includes answering the BCSS Questionnaire and recording any PRN medications. Subjects will complete their bi-weekly manual device transmissions and follow-up visits every three months post device insertion. Subjects will be followed until the last enrolled subject reaches their 12-month visit or until study closure, whichever occurs first. A STROBE diagram will show each of these stages of follow-up with categories for completed visits, missed visits, deaths and exits.

7.1.2 Clinical Investigation Plan (CIP) Deviations

Study deviations will result in corresponding Study Deviation eCRFs being completed. These deviations will be summarized with descriptive statistics including, for each type of deviation, number of occurrences in the study, and the number of subjects experiencing each type of deviation.

7.1.3 Analysis Sets

Enrolled subjects who have Reveal LINQ™ device successfully inserted, the LINQ™ HF investigational RAMware successfully downloaded to the device and have completed a first successful CareLink transmission will be included in the analysis of the primary objective.

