## 2. Glossary

Term	Definition
ADE	Adverse device effect
ADHF	Acute Decompensated Heart Failure
AE	Adverse event
AF	Atrial Fibrillation
ALLEViate-HF RAMware	Investigational software downloaded to the LINQ™ TruRhythm device in study subjects
BCSS	Breathlessness, Cough, and Sputum Scale
BNP	Brain natriuretic peptide
CFR	Code of Federal Regulations
CIP	Clinical Investigation Plan

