# Reveal LINQ™ for COPD Study Clinical Investigation Plan

Version 5.0,  
1-DEC-22

Page 9 of 79

Medtronic

Term	Definition
ICF	Informed consent form
ICM	Insertable cardiac monitor
ICMJE	International Committee of Medical Journal Editors
IDE	Investigational Device Exemption
IFU	Indications for Use
IPG	Implantable pulse generator
IRB	Institutional Review Board
LAR	Legally authorized representative
LINQ HF RAMware	Investigational software downloaded to the LINQ™ Pre-TruRhythm device in study subjects
MCT	Mobile cardiac telemetry
MedDRA	Medical Dictionary for Regulatory Activities
MiD	Monitoring in Dialysis
NSR	Non-significant Risk
NT-proBNP	N-terminal brain natriuretic peptide
PRN	'pro re nata' – as needed
RDC	Remote data capture
RR	Respiration rate
SADE	Serious adverse device effect
SAE	Serious adverse event
SAP	Statistical analysis plan
SC	Steering Committee
SCD	Sudden Cardiac Death
SDN	Software Distribution Network

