## 7.1.5 Medtronic Investigational RAMware

### 7.1.5.1 LINQ HF Investigational RAMware

The LINQ HF investigational RAMware is required to activate additional sensors in the Reveal LINQ ICM (pre-TruRhythm) to allow for collection of device data needed for potential detection of early COPD events. In addition to the existing diagnostic data normally stored in the device, the LINQ HF investigational RAMware enables the Reveal LINQ™ hardware to collect and store additional sensor data, including impedance, temperature, activity, R-R interval, R-wave amplitude, posture change count (based on z-axis accelerometer values) and x, y, and z-axis accelerometer measurements. The device

will collect and store this data every 60 minutes for impedance, temperature, activity, R-wave amplitude and every 5 minutes for R-R intervals, posture change count, and x, y, and z-axis accelerometer values. In addition, impedance measurements are collected when the Patient Assistant is used.

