## 7.1.5.2 ALLEVIATE-HF Investigational RAMware

The ALLEVIATE-HF investigational RAMware is required to activate sensors in the Reveal LINQ ICM with TruRhythm to allow for collection of device data needed for potential detection of early COPD events. In addition to the existing diagnostic data normally stored in the device, the ALLEVIATE-HF investigational RAMware enables the Reveal LINQ™ to record and store impedance, temperature, R-R interval, R-wave amplitude, x, y, and z-axis accelerometer measurements and posture change count periodically. The RAMware will calculate the respiration rate and will store daily impedance and respiration rate values.

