## 10.8 Implant

The LINQ™ insertion procedure must occur within 30 days of enrollment or baseline assessment and will be performed in accordance with the Medtronic Reveal LINQ™ implant instructions. The recommended implant locations are located in Figure 10 below. Physicians should follow the implant manuals when performing the Reveal LINQ™ implant.

[figure not shown]

Figure 10: Recommended Insertion Locations

After the Reveal LINQ™ device is inserted, the LINQ HF or ALLEViate-HF investigational RAMware will be downloaded to the device via the 2090 programmer depending on the type of the Reveal LINQ device (see Table 7 below).

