### 14.3.4 Determination of Subjects/Data for Analysis

Enrolled subjects who have Reveal LINQ™ device successfully inserted and have either the LINQ™ HF or ALLEViate-HF investigational RAMware successfully downloaded to the device and who have completed a first successful CareLink transmission.

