7.9.4 Determination of Subjects/Data for Analysis

Enrolled subjects who have Reveal LINQ™ device successfully inserted and have the LINQ™ HF investigational RAMware successfully downloaded to the device and who have completed a first successful CareLink transmission.

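### SAP 7.1.3 and 7.9.4 admit only LINQ HF RAMware subjects to the primary-objective analysis, whereas protocol 14.3.4 admits LINQ HF or ALLEViate-HF

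*SAP*

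**What the plan says.** **SAP.** Section 7.1.3 defines the set for the primary objective by device insertion together with "the LINQ™ HF investigational RAMware successfully downloaded to the device and have completed a first successful CareLink transmission will be included in the analysis". Section 7.9.4 states the same rule: subjects must "have the LINQ™ HF investigational RAMware successfully downloaded to the device". Sections 3, 6, 7.1.1 and 7.7 also name only LINQ HF, and ALLEViate-HF appears nowhere in the SAP text. Section 7.11 declares no change from the analysis planned in the CIP.

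**Protocol (version 5.0).** The matching section, 14.3.4, admits subjects who "have either the LINQ™ HF or ALLEViate-HF investigational RAMware successfully downloaded to the device". The remaining conditions, insertion and a first successful CareLink transmission, are the same in both documents.

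**The two RAMwares are separate products.** The glossary defines ALLEViate-HF RAMware as "Investigational software downloaded to the LINQ™ TruRhythm device in study subjects" and LINQ HF RAMware as "Investigational software downloaded to the LINQ™ Pre-TruRhythm device in study subjects". Section 7.1.5.2 adds: "The ALLEVIATE-HF investigational RAMware is required to activate sensors in the Reveal LINQ ICM with TruRhythm". Under section 10.8 the RAMware "will be downloaded to the device via the 2090 programmer depending on the type of the Reveal LINQ device", and Table 7 pairs each RAMware with one device type.

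**The concern.** The protocol and the SAP define different analysis sets for the only primary objective. A TruRhythm subject who is treated exactly as planned receives ALLEViate-HF, meets the protocol's definition and fails the SAP's.

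At stake are the analyses that use this set: the summaries of device data and the plots around each COPD event, the exploratory Kaplan-Meier and Cox analyses (SAP 7.9.3), and the baseline table for the analysed subset (SAP 7.6, which refers to 7.1.3). The baseline tables for all enrolled subjects and the safety summaries (SAP 7.10) are not tied to this set and are unaffected.

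Protocol 14.1 makes the SAP the full description of the analyses for the final report, and protocol 14.5 lists it among the measures against bias. Including ALLEViate-HF subjects at analysis would follow the protocol but depart from the written SAP. Leaving them out would do the reverse.

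**Working it through.** **1. Does anything in the SAP readmit ALLEViate-HF subjects?** The as-treated statement in SAP 7.2 does not widen a set that is defined by a named download. The procedure summary in 7.7 tabulates download success for LINQ HF only. Section 7.9.3 calls the signals Reveal LINQ HF data, but so does protocol 14.3.3, so that label proves nothing either way. The set rule is different: it names a RAMware product at the place where protocol 14.3.4 names two. The sample-size sentences show the same contrast. SAP 6 specifies LINQ HF, while protocol 14.4 refers to the investigational RAMware without naming one.

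**2. Where does the mismatch come from?** Other features of the SAP also differ from protocol version 5.0:

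| Feature | SAP | Protocol 5.0 | Changed in (protocol 19) |
|---|---|---|---|
| Diary | daily | weekly, or when symptoms change | 4.0 |
| In-office visit | required at 6 months | optional | 4.0 |
| RAMware | LINQ HF | LINQ HF or ALLEViate-HF | 4.0 |
| Last subject followed to | 12 months | 6 months | 5.0 |
| Total duration | 25 months | 33 months | 5.0 |

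The pattern fits an SAP written before version 4.0 and not revised since.

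**3. The plan's own projection.** The inputs in protocol 14.4 and SAP 6 are 60 subjects, 2 exacerbations per patient-year, 12 months, and 50% meeting the COPD event definition.

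- Exacerbations: 60 × 2 × 1 = 120, as stated.
- COPD events: 120 × 0.50 = 60, as stated.

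**4. Effect of the SAP rule.** Let f be the share of subjects with ALLEViate-HF. The documents do not give it, so the values below are assumptions. With equal event rates and equal follow-up, events kept = 60 × (1 − f).

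| f | Events kept | Events lost |
|---|---|---|
| 0 | 60 | 0 |
| 0.10 | 54 | 6 |
| 0.25 | 45 | 15 |
| 0.50 | 30 | 30 |
| 0.75 | 15 | 45 |

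**5. Unequal follow-up.** ALLEViate-HF entered at version 4.0, and all subjects are followed to a common end (protocol 6). Its recipients therefore probably have less follow-up. If k is the ratio of their mean follow-up to that of LINQ HF subjects, with equal event rates, the lost fraction of events is fk / (fk + 1 − f). This is below f whenever k < 1 and 0 < f < 1. As an illustration only, take 6 months against 12 months (k = 6/12 = 0.5) and f = 0.50: 0.25 / (0.25 + 0.50) = 0.33, instead of 0.50.

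**The case against.** The strongest reply is that this is an outdated document and not a decision about the analysis. The table of differences supports that. The current protocol states the intended set clearly, and a statistician who works from it would include both cohorts. A reader might infer that the sponsor chose to exclude TruRhythm subjects. The documents do not support that: the SAP gives no reason for such an exclusion and never mentions the second RAMware. Nor do they show that the statement in SAP 7.11 was wrong when written. The protocol version that the SAP was written against cannot be seen, so one can say only that the statement does not hold against version 5.0.

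The reply also has force on size. The share f is unknown and may be 0, and equal follow-up is doubtful. The study is exploratory, with no hypothesis, power or event target (protocol 14, 14.3.1 and 14.4), so to infer that it becomes underpowered or misses a required count would go too far.

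A further fair point is that replacing the set wording alone would pool unlike data. Protocol 7.1.5.1 describes impedance stored every 60 minutes and lists activity. Protocol 7.1.5.2 describes stored daily impedance and a calculated respiration rate, and does not list activity.

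None of this removes the contradiction. Version lag explains why the SAP rule is narrower, but the rule still excludes a cohort that the protocol includes.

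**Conclusion.** The contradiction holds on the text. Followed literally, SAP 7.1.3 and 7.9.4 remove every ALLEViate-HF subject, and that subject's adjudicated COPD events, from the primary-objective analyses, while protocol 14.3.4 keeps them. It should be corrected before the data are analysed.

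The size is unknown. Under equal event rates and follow-up the lost share of events equals f. With the shorter follow-up that is likely for ALLEViate-HF subjects, it would tend to be smaller. If no subject received ALLEViate-HF, nothing is lost. The conclusion rests on the two set definitions and on the pairing of RAMware with device type, not on any assumed value of f.

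**What to change.** All changes that are needed now are in the SAP:

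- In 7.1.3 and 7.9.4, take the condition from protocol 14.3.4: subjects must "have either the LINQ™ HF or ALLEViate-HF investigational RAMware successfully downloaded to the device".
- Align sections 3, 6 and 7.1.1, and in 7.7 tabulate download success for either RAMware.
- In 7.9.3, refer to Reveal LINQ derived data from either RAMware.
- Rewrite 7.11 after a comparison with protocol version 5.0. That comparison should also cover the other outdated features listed above.
- State how the two data sources are combined. Reduce signals that both RAMwares provide to a common daily value, which suits the daily averages already planned in 7.9.3. Show summaries and event plots by RAMware type as well as pooled, and label any signal that only one RAMware provides.

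The loose Reveal LINQ HF label in protocol 14.3.3 can wait for the next protocol revision, which would need sponsor and IRB/EC approval under section 16.6.

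The cost is SAP wording and one additional display by RAMware type. RAMware type should be identifiable from the device type and the insertion records. Protocol 7.11.2 says that installation is recorded on eCRFs but not that the type is, so this should be confirmed on the form.

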7.2 General Methodology

Data analysis will be performed by a Medtronic statistician or designee, and after all subject exit the study. All analyses will be performed on an “As Treated” basis. Any change to the data analysis methods

described in the protocol will require an amendment only if it changes a principal feature of the protocol. Any other change to the data analysis methods described in the protocol, and the justification for making the change, will be described in the clinical study report.

